5.4.1.2. After 12, 24, 36, and 48 Weeks Off Treatment

The HBsAg seroclearance will be evaluated at each of the following timepoints separately: 12, 24, 36 and 48 Weeks after stopping all study interventions at any time. Participants with HBsAg seroclearance 12, 24, 36 and 48 Weeks, respectively, after stopping all study interventions and without restarting NA treatment thereafter, will be considered as having achieved this endpoint regardless of meeting the NA stopping criteria and of treatment duration. Of note, HBsAg seroclearance may be achieved prior to the Week 12, 24, 36, or 48, respectively, but must be observed at the given week of interest.

The CRF pages of ‘Treatment Disposition of JNJ-3989’, ‘Treatment Disposition of JNJ-6379’ and ‘Treatment Disposition of ETV, TDF or TAF’ will be checked to ensure all treatment actually

stopped. In addition, the CRF page of 'NA Re-treatment Criteria Assessment' will be checked to ensure no NA re-treatment required within 12, 24, 36 and 48 Weeks, respectively, after stopping all study interventions.

If the HBsAg value at 12 weeks after stopping all study interventions is missing, the next available observation will be used. The next non-missing lab test no later than 24 weeks after stopping all study interventions will be imputed.

If the HBsAg value at 24/36 weeks after stopping all study interventions is missing, the LOCF in conjunction with the next available observation imputation approach will be used. The available non-missing lab test closest to 24/36 weeks after stopping all study interventions which is no earlier/later than 12 weeks from the actual time point of interest (12/24 and 36/48 weeks after stopping all study interventions, respectively) will be imputed.

If the HBsAg value at 48 weeks after stopping all study interventions is missing, the LOCF imputation approach will be used. The last available lab test no earlier than 36 weeks after stopping all study interventions will be carried forward.

The following analysis will be repeated for 4 different timepoints: 12, 24, 36, and 48 weeks after stopping all study interventions. The proportion of participants who achieve HBsAg seroclearance at a given point (e.g. 12 weeks after stopping all study interventions) will be summarized stratified by meeting the NA completion criteria (yes, or no) at the time when they stopped all study interventions.

5.4.2. Suppressed HBV DNA

HBV DNA <LLOQ will be evaluated over all time points when assessed, with emphasis at the following time points:

- 12 weeks after stopping all study interventions (regardless when intervention was stopped) without restarting NA treatment, and
- 24 weeks after stopping all study interventions (regardless when intervention was stopped) without restarting NA treatment, and
- 36 weeks after stopping all study interventions (regardless when intervention was stopped) without restarting NA treatment, and
- 48 weeks after stopping all study interventions (regardless when intervention was stopped) without restarting NA treatment

Proportions will be analyzed using the Mantel-Haenszel test and 90% CIs stratified for treatment history status and screening HBeAg status.

HBV DNA TND will be evaluated at the same time points with the same methodology described above.

5.4.2.1. Suppressed HBV DNA After Stopping Study Interventions

The proportion of participants with HBV DNA <LLOQ will be evaluated at each of the following time points separately: 12, 24, 36 and 48 weeks, respectively, after stopping all study interventions at any time during the study and without restarting NA treatment thereafter.

In addition, the proportion of participants with HBV DNA TND will be evaluated at each of the following time points separately: 12, 24, 36 and 48 weeks, respectively, after stopping all study interventions at any time during the study and without restarting NA treatment thereafter will be calculated and summarized separately.

If the HBV DNA value at 12 weeks after stopping all study interventions is missing, the next available observation will be used. The next non-missing lab test no later than 24 weeks after stopping all study interventions will be imputed.

If the HBV DNA value at 24 weeks after stopping all study interventions is missing, the LOCF in conjunction with the next available observation imputation approach will be used. The available non-missing lab test closest to 24 weeks after stopping all study interventions which is no earlier/later than 12 weeks from the actual time point of interest (12 and 36 weeks after stopping all study interventions, respectively) will be imputed.

If the HBV DNA value at 36 weeks after stopping all study interventions is missing, the LOCF in conjunction with the next available observation imputation approach will be used. The available non-missing lab test closest to 36 weeks after stopping all study interventions which is no earlier/later than 12 weeks from the actual time point of interest (24 and 48 weeks after stopping all study interventions, respectively) will be imputed.

If the HBV DNA value at 48 weeks after stopping all study interventions is missing, the LOCF imputation approach will be used. The last available lab test no earlier than 36 weeks after stopping all study interventions will be carried forward.

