9.4.1.3. Other Secondary and Exploratory Efficacy Endpoints

Descriptive statistics will be used for all efficacy endpoints which will be summarized by intervention arm. Comparisons among intervention arms will be done with no adjustment for multiplicity. Specific key selected endpoints may be analyzed using suitable categorical data

approaches (eg, Cochran-Mantel-Haenszel [CMH] or logistic regression for proportions or other categorical type of endpoint), longitudinal repeated measures models (eg, for continuous types of variables), or survival analysis based on the Kaplan-Meier estimates (for time-to-event variables), as appropriate. Details will be described in the SAP.

The efficacy of the study intervention during the follow-up phase will be evaluated. The proportion of participants with HBsAg seroclearance 48 weeks after completion of all study intervention at Week 48, the proportion of participants with HBV DNA <LLOQ 24 and 48 weeks after completion of all study intervention at Week 48, the proportion of participants meeting the NA treatment completion criteria during follow-up, the proportion of participants with HBsAg seroclearance 24 and 48 weeks after completion of NA treatment at any time during follow-up, the frequency of flares, and the proportion of participants requiring NA re-treatment during follow-up will be tabulated by intervention arm. The comparison among the intervention arms will be done using CMH chi-square test stratified by HBeAg status at screening (positive versus negative) and treatment history (naïve or NA suppressed) and corresponding 90% CIs without adjustment for multiple intervals.

The proportion of participants who reach HBV DNA undetectability after re-start of NA treatment during follow-up will also be tabulated by intervention arm and the comparison among the intervention arms will be done using the CMH chi-square test as described above.

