
 To explore efficacy as measured by HBV RNA and HBcrAg during study intervention and follow-up. 	
 Changes from baseline in HBV RNA and HBcrAg levels. Time to reach undetectability of HBV RNA and HBcrAg.

 To explore the impact of the baseline HBeAg and treatment status factors on efficacy as measured by primary and secondary endpoints. 	
 Proportion of participants meeting the NA treatment completion criteria at Week 48. Proportion of participants with HBsAg seroclearance 24 weeks after completion of all study intervention at Week 48. Proportion of participants with HBsAg seroclearance 48 weeks after completion of all study intervention at Week 48. Proportion of participants with HBV DNA <LLOQ 24 and 48 weeks after completion of all study intervention at Week 48. Proportion of participants meeting the NA treatment completion criteria during follow-up. Proportion of participants with HBsAg seroclearance 24 and 48 weeks after completion of NA treatment at any time during follow-up. Frequency of flares. Proportion of participants requiring NA re-treatment during follow-up.

 To explore the association between viral and host baseline factors with efficacy and safety. 	
 Correlation of viral and host baseline characteristics (such as HBV genotype, baseline HBV DNA levels, age, gender, body mass index [BMI]) with selected efficacy and safety variables.

 To explore changes in the HBV genome sequence during study intervention and follow-up. 	
 Emergence of intervention-associated mutations.

Objectives	Endpoints

 To explore the effect of any baseline variation in the HBV genome on efficacy. 	
 Correlation of HBV genome sequence with selected efficacy parameters.

 To explore HBV-specific T-cell responses during study intervention and follow-up. 	
 Changes from baseline in HBV-specific peripheral blood T-cell responses.

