5.4.1. HBsAg Seroconversion

HBsAg seroclearance will be evaluated over all time points when assessed, with emphasis at the following time points:

- at Week 48
- at Week 96 (ie, 48 weeks after completion of all study interventions at Week 48) without restarting NA treatment,

- 12 weeks after stopping all study interventions (regardless when intervention was stopped) without restarting NA treatment, and
- 24 weeks after stopping all study interventions (regardless when intervention was stopped) without restarting NA treatment, and
- 36 weeks after stopping all study interventions (regardless when intervention was stopped) without restarting NA treatment, and
- 48 weeks after stopping all study interventions (regardless when intervention was stopped) without restarting NA treatment

Proportions at the time points listed in the above bullets will be analyzed using the Mantel-Haenszel test and 90% CIs stratified for treatment history status and screening HBeAg status.

5.4.1.1. At Week 48 and At Week 96

The proportion of participants achieving HBsAg seroclearance at EOT (Week 48), and at Week 96 (48 weeks after completion of all study interventions at Week 48) will be summarized by intervention arm. A participant will be defined as responder at Week 96 (with HBsAg seroclearance 48 weeks after completion of all study intervention at Week 48) if he/she has completed 48 weeks of treatment AND met the criteria for stopping NA treatment at Week 48 AND not required NA re-treatment between Week 48 and Week 96 AND had HBsAg seroclearance at Week 96. If the HBsAg value at Week 96 is missing, the LOCF approach will be used with the condition that no value earlier than Week 84 may be carried forward.

Those participants who did not meet the NA stopping criteria at Week 48 OR did not complete 48 weeks of treatment OR did not reach seroclearance at Week 96 will be defined as non-responders for Week 96. The participants who has no HBsAg value between Week 84 and 96 or required NA re-treatment prior to Week 96 will be considered as non-responder as well.

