5.4.5.4. HBV DNA Thresholds

The values and decreases from baseline of HBV DNA will be summarized by treatment history (not currently treated and virologically suppressed).

The following cut-offs for HBV DNA values and decreases from baseline will be used in separate summaries over time by intervention arm. The number and proportion of participants who meet those HBV DNA thresholds during the study will be summarized descriptively by intervention arm and analysis phase over time.

Thresholds for **HBV DNA** values:

- < LLOQ for target detected and not detected
- < LLOQ for target not detected
- < LLOQ for target detected
- <60 IU/mL
- <100 IU/mL
- <200 IU/mL

- <1000 IU/mL
- <2000 IU/mL
- <20000 IU/mL

Thresholds for **HBV DNA** decreases from baseline:

- $\geq 1 \log_{10}$ IU/mL
- $\geq 2 \log_{10}$ IU/mL
- $\geq 3 \log_{10}$ IU/mL
- $\geq 4 \log_{10}$ IU/mL
- $\geq 5 \log_{10}$ IU/mL

Cumulative percentage of participants achieving any given decrease from baseline in HBV DNA at Week 72 and at Week 96, separately, will be presented graphically.

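### SAP 5.4.2 and 5.4.2.1 define off-treatment HBV DNA <LLOQ only for stopping at any time; the listed secondary endpoint, anchored to stopping everything at Week 48, has no analysis rule

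*SAP*

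**What the plan says.** Protocol 9.4.1.3 lists, among the follow-up endpoints to be compared between arms by a stratified CMH test, "the proportion of participants with HBV DNA <LLOQ 24 and 48 weeks after completion of all study intervention at Week 48". The same section separately lists HBsAg "seroclearance 24 and 48 weeks after completion of NA treatment at any time during follow-up". The protocol therefore treats the two anchors as different endpoints, and it uses the any-time anchor for HBsAg only.

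The SAP keeps the Week 48 anchor in its objectives table (1.1), both as a secondary endpoint and again under the baseline-factor objective: "Proportion of participants with HBV DNA <LLOQ 24 and 48 weeks after completion of all study intervention at Week 48".

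The SAP analysis sections differ. Section 5.4.2 opens with "HBV DNA <LLOQ will be evaluated over all time points when assessed, with emphasis at the following time points". The listed time points are 12, 24, 36 and 48 weeks off treatment, each worded like "24 weeks after stopping all study interventions (regardless when intervention was stopped) without restarting NA treatment". Section 5.4.2.1 repeats the any-time anchor: "after stopping all study interventions at any time during the study and without restarting NA treatment thereafter".

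For HBsAg the SAP specifies both versions. The Week 48 anchor appears in 5.3.1 (Week 72) and in 5.4.1 and 5.4.1.1: "at Week 96 (ie, 48 weeks after completion of all study interventions at Week 48) without restarting NA treatment". The any-time version is in 5.4.1.2.

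**The concern.** A programmer who follows 5.4.2.1 will produce a table that looks like the listed endpoint but answers another question. Protocol 2.1 sets the study up to assess a fixed 48-week course, with off-treatment HBV DNA suppression among the responses of interest. The anchored endpoint addresses that directly: every arm is judged on the same Week 44 laboratory test and the same calendar of visits afterwards.

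The any-time version changes three things:

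- **Who can count.** Early discontinuers and people who stop NA during follow-up join those who stopped at Week 48. Protocol 4.1 and 7.1 allow NA to be stopped after early discontinuation on investigator judgement, so some of these participants need not have met the completion criteria.
- **Opportunity to count.** After Week 48, how often a participant can qualify to stop NA depends on the arm's visit schedule.
- **When it is complete.** At the Week 72 and Week 96 analyses the anchored endpoint is fully observed. Someone who stops NA at Follow-up Week 48 (Week 96) reaches 24 weeks off treatment only at Week 120.

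**Working it through.** The documents give no power, sample size or alpha figure for this endpoint, so there is no stated number to reproduce. The check compares the SAP sections and then counts from the schedules.

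**1. Does any other SAP section supply the anchored analysis?**

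- 5.4.2.2: suppression after NA re-treatment. A different question.
- 5.4.5.4: "participants who meet those HBV DNA thresholds during the study will be summarized descriptively by intervention arm and analysis phase over time". Counts are by visit and do not require treatment to have stopped, so participants still on or back on NA are included.
- 5.4.6 and 5.4.7 (multiple markers, partial cure): anchored to stopping all interventions, not to Week 48.
- 5.4.5.1: individual HBV DNA profiles by Week 48 completion-criteria status. This displays the relevant group but gives no proportion and applies no re-treatment rule.

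None gives a Week 48-anchored HBV DNA <LLOQ proportion. Section 5.4.2.1 also states no denominator. Unlike 5.4.1.2 for HBsAg, it does not split results by whether the completion criteria were met at stopping.

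**2. Scheduled chances to qualify for stopping NA after Week 48** (Protocol 1.3.2 and 6.6; the last qualifying test is at Follow-up Week 42, or Week 36 in Arm 6)

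- Arms 1-5, NA continued: Follow-up Weeks 2, 4, 6, 8, 12, 16, 20, 24, 30, 36, 42 = 11 checks.
- Arm 6, NA continued: Follow-up Weeks 12, 24, 36 = 3 checks.

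**3. Time since investigational treatment at the 24-week assessment, for participants who completed the 48-week course**

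NA can stop from Week 48 to Follow-up Week 48, which is Week 48 + 48 = 96. The assessment then falls between Week 48 + 24 = 72 and Week 96 + 24 = 120.

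- Since the last oral JNJ-6379 dose (Week 48): 72 − 48 = 24 to 120 − 48 = 72 weeks.
- Since the last scheduled JNJ-3989 injection (Week 44, Protocol 1.3.1): 72 − 44 = 28 to 120 − 44 = 76 weeks.

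Under the Week 48 anchor these are single values, about 24 and 28 weeks.

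**4. Illustration of how far the two quantities can differ**

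Protocol 9.2 plans on 25% to 35% of the 90 participants in the JNJ-3989 100 mg + NA arm meeting the criteria at Week 48: 0.25 × 90 = 22.5 to 0.35 × 90 = 31.5. Assume, with no support from the documents, that a further 5% to 15% of the arm stop NA at another time: 4.5 to 13.5 participants. With the whole arm as denominator, the highest attainable proportion moves:

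- from 25% to (22.5 + 4.5)/90 = 30% up to (22.5 + 13.5)/90 = 40%;
- from 35% to (31.5 + 4.5)/90 = 40% up to (31.5 + 13.5)/90 = 50%.

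These are ceilings, not expected results. The two eligible groups coincide only if nobody stops all treatment at a time other than Week 48.

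**The case against.** The SAP still lists the endpoint, and 5.4.2 covers every assessed visit, which includes Weeks 72 and 96. Week 48 stoppers are a subset of the any-time group, so the data are there. SAP Section 5 also plans efficacy results by analysis phase where applicable. Under SAP Table 1, people who stop NA by Week 48 stay in the Follow-up phase, while those who complete NA later move to Extended Follow-up. A by-phase display would therefore separate the late stoppers. Finally, this is one of many other secondary endpoints in a Phase 2b study, and the off-treatment endpoint used for dose and regimen selection, functional cure at Week 72, is correctly anchored.

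Most of this stands and limits the point. A reader might infer that the endpoint was dropped or cannot be estimated; the documents do not support that. A reader might also infer that the any-time analysis favours the active arms by a known amount. The unequal schedule is a fact, but nothing in the documents shows its effect on this endpoint. Nor does the any-time version generally mix durations of investigational treatment: follow-up stoppers who completed the course had the same fixed 48 weeks, and only their NA duration differs. Mixed investigational duration arises only through early discontinuers.

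The by-phase argument does not close the gap. The phase split applies only where applicable, 5.4.2.1 does not ask for it, and it would still leave stoppers before Week 48 pooled with those at Week 48. Protocol 9.4.1.3 leaves details to the SAP, but the anchor is part of the endpoint definition, not a detail.

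**Conclusion.** The point holds as a mismatch between a listed endpoint and its specified analysis. The protocol and the SAP objectives ask about stopping everything at Week 48; SAP 5.4.2 and 5.4.2.1 specify only stopping at any time. The SAP is thus inconsistent with the protocol and with itself, and its amendment history gives no rationale. Followed as written, it estimates a different quantity, with 11 against 3 scheduled opportunities to qualify after Week 48.

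The numerical effect is unknown, since it depends on how many participants stop at other times, and no direction or size of bias is claimed. The week ranges above apply only to participants who completed the 48-week course. The primary and key secondary analyses are unaffected. The sponsor should correct this, but it does not threaten the study's main conclusions.

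**What to change.** Add to SAP 5.4.2 an HBV DNA <LLOQ responder definition at Week 72 and at Week 96, parallel to 5.3.1 and 5.4.1.1:

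- met the NA completion criteria and stopped all study treatment at Week 48;
- no NA re-treatment up to the visit;
- HBV DNA <LLOQ at the visit.

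Use the same analysis-set denominator as the HBsAg analyses (mITT is the SAP's primary efficacy set), with everyone else a non-responder. State a missing-data rule consistent with the HBsAg analyses. For Week 48 stoppers, the windows already in 5.4.2.1 translate to Weeks 60-84 for the Week 72 visit and no earlier than Week 84 for Week 96. These match the LOCF windows in 5.3.2.2.1.2 and 5.4.1.1. Compare arms with the stratified Mantel-Haenszel method and 90% CIs already planned, and label the any-time analysis as supportive.

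The cost is one paragraph and two table columns, with no new data. SAP Amendment 2 refers to interim analyses already done, and all of these follow sponsor unblinding. The added rule should therefore copy the HBsAg wording rather than be designed afresh, and its date should be stated. If the rule already exists in the Data Presentation Specification that the amendment mentions, transfer it from there.

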5.4.2.2. Suppressed HBV DNA After NA Re-Treatment

Proportion of participants who reach HBV DNA <LLOQ after NA re-treatment during follow-up will be summarized by intervention arm. In addition, proportion of participants who reach HBV DNA TND after NA re-treatment during follow-up will be summarized by intervention arm.

Re-start of NA treatment during follow-up will be checked according to the CRF page of 'NA Re-treatment Criteria Assessment' in follow-up phase. In addition, the CRF page of 'Study Drug Administration for ETV, TDF or TAF' will be checked to ensure the actual re-start of NA treatment during follow-up.

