	Proportion of HBeAg-positive participants with HBeAg** levels and/or changes from baseline below/above different cut-offs.				
	• Proportion of participants with HBV DNA levels and/or changes from baseline below/above different cut-offs (eg, <lloq assay).<="" of="" th="" the=""></lloq>				
	• Proportion of participants with ALT decrease and normalization.				
To evaluate the frequency of virologic breakthrough.	Proportion of participants with virologic breakthrough.				
To evaluate the efficacy of NA re-treatment in participants who meet the criteria for NA re-treatment.	Proportion of participants who reach HBV DNA undetectability after re-start of NA treatment during follow-up.				
• To evaluate the PK of JNJ-3989 (JNJ-3976 and JNJ-3924), JNJ-6379, and NA, as applicable.	PK parameters of JNJ-3989 (JNJ-3976 and JNJ-3924), JNJ-6379, and NA, as applicable.				
Exploratory					
• To explore changes in the severity of liver disease at the end of follow-up versus screening/baseline.	Changes in fibrosis (according to Fibroscan liver stiffness measurements).				
To explore the relationship between PK parameters (JNJ-3989 and/or JNJ-6379 and/or NA) and selected pharmacodynamic (PD) parameters of efficacy and/or safety, as applicable.	Relationship between various PK parameters (JNJ-3989 and/or JNJ-6379 and/or NA) and selected efficacy and/or safety endpoints, as applicable.				
To explore efficacy as measured by HBV RNA and HBcrAg during study intervention	Changes from baseline in HBV RNA and HBcrAg levels.				
and follow-up.	Time to reach undetectability of HBV RNA and HBcrAg.				
To explore the impact of the baseline HBeAg and treatment status factors on efficacy as	Proportion of participants meeting the NA treatment completion criteria at Week 48.				
measured by primary and secondary endpoints.	Proportion of participants with HBsAg seroclearance 24 weeks after completion of all study intervention at Week 48.				
	Proportion of participants with HBsAg seroclearance 48 weeks after completion of all				

Objectives	Endpoints				
	study intervention at Week 48.				
	• Proportion of participants with HBV DNA <lloq 24="" 48="" 48.<="" after="" all="" and="" at="" completion="" intervention="" of="" respectively,="" study="" th="" week="" weeks,=""></lloq>				
	Proportion of participants meeting the NA treatment completion criteria during follow-up.				

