- **Double-blind study intervention phase:** from Day 1 (ie, baseline) up to Week 48.
- **Follow-up phase:** for 48 weeks after the end of investigational intervention. For participants who complete NA treatment during follow-up, the follow-up phase will be extended to 48 weeks after the end of NA treatment. The follow-up phase has a maximum duration of 96 weeks.

The duration of individual study participation will be between 100 and 150 weeks.

At Week 48 or at time of early discontinuation, it will be communicated to the investigators whether the participants were allocated to either an investigational arm (Arms 1 to 5) or the control arm (Arm 6) to allow the correct follow-up visit schedule to be followed (see Schedule of Activities). Only at Week 72, randomization codes (for Arms 1 to 5) will be fully disclosed to the investigators. The sponsor will be fully unblinded for the primary analysis at Week 48 (see Section 9).

Participants will be considered to have completed the study if they have completed the assessments of the end of study (EOS) visit ([Extended] Follow-up Week 48). After completing this study, participants may be invited to enroll into a long-term follow-up study.

Efficacy will be evaluated using different parameters including HBsAg and HBeAg (see Section 8.1).

Safety and tolerability, including (S)AEs, laboratory assessments, ECGs, vital signs, and physical examination, will be assessed throughout the study from the time of signing the informed consent form (ICF) until completion of the last study-related activity (see Section 8.2).

Three PRO instruments, including the HBOOL scale, ³² an HBV-specific self-stigma PRO scale, and the PGIC scale^{11,18} will be used to exploratively assess the impact of study intervention on participants' HRQoL, self-stigma level, and impression of change (see Section 8.1.2).

Samples for HBV genome sequencing will be taken at the time points indicated in the Schedule of Activities (see Section 8.1.1).

A population PK analysis will be performed based on the available data for JNJ-3989, JNJ-6379 and, optionally, NA, potentially in combination with data from a selection of Phase 1 and 2

studies. PK parameters in participants undergoing intensive PK sampling will be calculated via noncompartmental methods (see Section 8.5).

Pharmacokinetic/pharmacodynamic relations will be explored (see Section 8.6).

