^{*} At least 4 weeks apart frequency of visits as described above

confirmatory test results will become available. This should ensure that the participant can immediately re-start NA treatment if indicated, upon direct confirmation by the investigator.

In case NA treatment is re-started, participants will be followed until the end of the study or until clinical stabilization, whichever comes later.

NA re-treatment criteria and monitoring after stopping of NA are presented graphically in Section 10.14, Appendix 14.

Management of intervention-emergent ALT/AST elevations is discussed in Section 8.3.6.

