5.4.13. ALT Normalization After NA Re-Treatment

Proportion of participants who have $ALT \geq ULN$ before NA re-treatment and reach ALT normalization after NA re-treatment during follow-up will be summarized by intervention arm.

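### HBV DNA re-suppression after NA re-start (SAP 5.4.2.2) has no time origin and no entry level, so the proportion mixes re-treatment efficacy with time observed after re-start

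*SAP*

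**What the plan says.** Protocol Section 3 lists a secondary objective: "To evaluate the efficacy of NA re-treatment in participants who meet the criteria for NA re-treatment". Its only endpoint is re-suppression of HBV DNA after NA re-start. Protocol 9.4.1.3 plans: "The proportion of participants who reach HBV DNA undetectability after re-start of NA treatment during follow-up will also be tabulated by intervention arm", and compares arms by the stratified CMH test.

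SAP 5.4.2.2 reads: "Proportion of participants who reach HBV DNA <LLOQ after NA re-treatment during follow-up will be summarized by intervention arm", with a second summary for target not detected (TND). The rest of that section concerns CRF pages, which "will be checked to ensure the actual re-start of NA treatment during follow-up".

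SAP 5.4.13 is the parallel ALT endpoint. It requires ALT at or above ULN "before NA re-treatment and reach ALT normalization after NA re-treatment during follow-up will be summarized by intervention arm".

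Follow-up runs "for 48 weeks after the end of investigational intervention" (protocol 4.1). For participants who stop NA during follow-up, "the follow-up phase will be extended to 48 weeks after the end of NA treatment". Protocol 6.7 adds: "In case NA treatment is re-started, participants will be followed until the end of the study or until clinical stabilization, whichever comes later".

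**The concern.** The CRF checks confirm that NA was re-started. They do not fix how long the participant was observed afterwards, or whether HBV DNA was quantifiable at that moment. No other section fills either gap:

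- The 12-, 24-, 36- and 48-week time points and imputation rules in SAP 5.4.2 and 5.4.2.1 apply only to participants who have not restarted NA.
- The time-to-undetectability analysis in SAP 5.5.3.1 starts its clock at first study intake.

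A participant who re-starts late, and whose HBV DNA is still falling at the last visit, has not reached <LLOQ. A participant already <LLOQ at re-start satisfies the definition at the next visit. Two arms with equally effective re-treatment can therefore show different proportions because their re-starts fell at different times. The CMH test stratifies by HBeAg status and treatment history, not by time since re-start. What is at stake is the reading of the one endpoint that answers the re-treatment objective.

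**Working it through.** The documents give no expected rate, sample size or power for this endpoint, so there is no stated figure to reproduce. The check has three parts.

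**1. Observation left after re-start.** Counting weeks from NA stop and ignoring any extra follow-up, time left = 48 - re-start week. Re-start at Week 8 leaves 40 weeks, Week 24 leaves 24, Week 36 leaves 12 and Week 44 leaves 4. Protocol 6.6 also asks investigators to consider re-start at the end-of-study visit, which leaves none.

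**2. Effect of unequal observation.** All inputs here except the 48 weeks are assumptions. Every participant who re-started is counted, re-start week w is uniform on 8 to 46, and everyone eventually re-suppresses. Time to <LLOQ is lognormal with median m and log-scale SD 0.4.

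Reported proportion = average over w of Φ(ln((E - w)/m)/0.4), where E is the last week of observation. The true proportion is 100%.

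| Median m (weeks) | E = 48 | E = 60 (12 further weeks assumed) |
|---|---|---|
| 4 | 94% | 100% |
| 8 | 82% | 99% |
| 12 | 71% | 96% |
| 16 | 60% | 88% |
| 24 | 39% | 69% |

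For a contrast between equally effective arms, let one re-start uniformly in Weeks 8-24 and the other in Weeks 20-46:

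- Median 16 weeks: about 94% against 43% at E = 48, and 99% against 83% at E = 60.
- Median 4 weeks: 100% against 91% at E = 48, and no gap at E = 60.

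A second model gives the same pattern. Take exponential time, so the proportion is 1 - 0.5^((48 - w)/m). One arm has 80% of re-starts at Week 8 and 20% at Week 36; the other has the reverse. For m = 12:

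- Week 8 gives 1 - 0.5^(40/12) = 0.901 and Week 36 gives 1 - 0.5^(12/12) = 0.500.
- The arms show 0.8 x 0.901 + 0.2 x 0.500 = 0.821 and 0.2 x 0.901 + 0.8 x 0.500 = 0.580, a gap of 24 points with equal efficacy.
- For m = 4, 8 and 24 the gap is 7, 19 and 24 points.

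**3. Effect of no entry level.** Protocol 6.7 lists five re-start criteria. Three require HBV DNA above 2,000 (with ALT >5x ULN), 20,000 or 100,000 IU/mL, far above the LLOQ of 20 IU/mL. The other two, decreasing liver function and HBeAg seroreversion, carry no HBV DNA condition, and neither does re-start at the investigator's discretion. If a share q is already <LLOQ at re-start and p is the rate among the rest, the reported rate is q + (1 - q)p:

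- q = 10%: 50% becomes 0.10 + 0.90 x 0.50 = 55%, and 90% becomes 91%.
- q = 30%: 50% becomes 65%, and 90% becomes 93%.

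The documents give no value for q.

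**The case against.** Several points on the other side stand.

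- **Follow-up after re-start is not cut at Week 48.** Protocol 6.7 extends it to clinical stabilization where that is later. The E = 60 column shows how far this could help. It does not close the gap, because the extension has no fixed length and the protocol does not define stabilization as HBV DNA <LLOQ.
- **The denominator is not written down.** The objective concerns participants who meet the re-treatment criteria, and SAP 5.4.2.2 consults the criteria page, so discretionary re-starts may be excluded. Liver-function and HBeAg re-starts would remain.
- **Timing is visible elsewhere.** SAP 5.4.4 summarizes actual re-starts over time by arm, and SAP 4.6 counts re-treatment weeks in NA exposure. A reader could see an imbalance but could not correct this proportion for it.
- **The CMH test is in the protocol only.** SAP 5.4.2.2 summarizes by arm and names no test. SAP 5.4 still foresees comparisons of other secondary endpoints, without multiplicity adjustment.

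A reader might go further and infer that the proportion reflects when participants re-started and says nothing about whether re-treatment works. The documents do not support that. Under the exponential model, with re-start at Week 12 in both groups, medians of 8 and 24 weeks give 1 - 0.5^(36/8) = 96% and 1 - 0.5^(36/24) = 65%. The measure still responds to efficacy when timing is equal. Nor can one say that the rate is simply biased downward, because counting participants already <LLOQ pushes it up.

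**Conclusion.** The point holds as a mixture of efficacy and observation time, with a smaller second problem of participants who may already be <LLOQ at re-start. The net direction is unknown. The size depends on re-start timing, time to re-suppression and the length of follow-up to stabilization, none of which the documents supply. Within the assumptions shown, a true 100% is reported anywhere from 39% to 100%. With fast suppression or appreciable extra follow-up the distortion is small; with slow suppression and late re-starts it is large. Any difference in re-start timing between arms is likewise assumed. This is one secondary endpoint of a Phase 2b study, and neither the primary nor the key secondary result depends on it. The change is worth making because the better analysis uses data already collected and methods the SAP already applies.

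**What to change.** In SAP 5.4.2.2:

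- Define the population as participants who actually re-started NA and whose last HBV DNA value on or before re-start was >=LLOQ. SAP 5.4.13 and 5.5.3.1 already set an entry level of this kind.
- Report Kaplan-Meier cumulative incidence of HBV DNA <LLOQ, and of TND, from the re-start date, censored at the last HBV DNA result. Give estimates at 12 and 24 weeks after re-start and numbers at risk by arm. SAP 5.4.3.3 and 5.4.14.2 already use Kaplan-Meier.

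Use the same time-from-re-start form in SAP 5.4.13. Base any between-arm comparison on these estimates instead of CMH on the crude proportion, and record this as a change from protocol 9.4.1.3.

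The cost is SAP wording plus that recorded departure; re-start dates and HBV DNA results are already collected. The drawback is precision: few participants may remain at risk by 24 weeks, so by-arm estimates may be imprecise.
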